Assessment	Baseline	Enrollment ^b (within 48 hrs of onset)	6 hours from dose	12 hours from enrollment	6 hours from dose	24 hours from enrollment	6 hours from dose	36 hours from enrollment	6 hours from dose	72 hours from enrollment	Days 3-6	Day 7	Discharge	Follow-up
Inclusion/ exclusion criteria	X ^a													
Consent Process	X ^a													
Patient demographics	X ^a													
Medical history	X ^a													
Clinical Assessment														
GCS	X ^c					X ^c				X ^c		X ^c	X ^c	X ⁱ
APACHE II	X ^c													
mRS	X ^c												X ^c	X ⁱ
ICH	X ^c													
RIFLE	X ^c												X ^c	X ⁱ
Imaging														
CT scan (non- contrast)	X ^d					X ^d				X ^d		X ^d		X ⁱ
Study Drug														
Conivaptan (20mg)		X ^f		X ^f		X ^f		X ^f						
Laboratory Tests														
Comprehensive metabolic Panel	X		X ^e		X ^e		X ^e		X ^e					
Magnesium	X		X ^e		X ^e		X ^e		X ^e					
Phosphorus	X		X ^e		X ^e		X ^e		X ^e					
EMR Data Collection^h														
Vital signs	X		X	X	X	X	X	X	X	X	X	X	X	
ICP monitoring	X		X	X	X	X	X	X	X	X	X	X		
Mannitol monitoring	X		X	X	X	X	X	X	X	X	X	X		
Sodium monitoring	X		X	X	X	X	X	X	X	X	X	X		
Medication log	X					X					X	X		
Cardiac monitoring	X		X	X	X	X	X	X	X	X	X	X		
Intake/Output	X					X				X	X	X		
Adverse event log	X	X	X	X	X	X	X	X	X	X	X	X	X	X ⁱ

^aOccurs prior to enrollment. Other standard-of-care activities that will have occurred (between hospital arrival to 6 hrs post-arrival): 1) CT +/- CTA/CTV, 2) identify and correct coagulopathy, 3) identify and correct blood pressure (BP), 4) identify and correct ICP, and 5) admission to Neuro-ICU.

^bEnrollment needs to occur within 48 hrs from initial symptoms.

^cClinical assessments can be study only or standard-of-care activities with a time window of +/- 6 hours.

^dAdmission and 24-hr stability CT scans are standard-of-care. Additional CT scans, other than the study related 72-hr and 7-day (168 hours) scans, may be done as clinically indicated by treating physician. All scans have a time window of +/- 8 hours.

^eDependent on conivaptan dose. Each needs to be drawn and analyzed 6 hours after each conivaptan dose. However, these labs may be done sooner (e.g., 2 hours after a conivaptan dose) based on the patient's progress/need and/or the attending physician's direction. Otherwise, standard-of-care labs (e.g., BMP) are drawn and analyzed every 12 hrs during the first 72 hrs after admission, followed by daily draws and analyses.

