^fDependent on when the 1st of the 4 doses was started.

^hStandard-of-care information collected as part of normal clinical practice will be recorded from the electronic medical record. Information may be recorded on a daily basis or after the protocol is complete.

ⁱFollow-up visits will be conducted as part of normal clinical practice and information recorded, if available, from the electronic medical record. Three month post-discharge follow-up visits are standard-of-care.

Note: Training and informational sessions covering all aspects of the study (e.g., patient enrollment, treatment, ordering of lab tests, data collecting, etc.) will be held prior to the start of the study.

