 5. Development of central pontine demyelination, expansion of initial ICH, new ICH or stroke.

- **Cardiac tolerability:**
 1. Troponin values.
 2. Development of new arrhythmia during ICU stay.

- **Pulmonary tolerability:**
 1. Development of pulmonary edema as determined by chest X-ray.
 2. Average PO₂, FiO₂, A-a gradient.

- **Renal tolerability:**
 1. Change in renal function/urine output. RIFLE criteria will be used to assess for development of renal dysfunction (Appendix 1).
 2. Need for renal replacement therapy (RRT).

- **Infectious tolerability:**
 1. Compare rates of BSI, VAP/HAP, UTI, and sepsis.

- In-hospital mortality stratified by APACHE II, GCS, and ICH Score.

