7.1 Risks and Benefits

7.1.1 Potential risks

Potential risks associated with conivaptan may include hypotension, excessive rise in serum sodium, development of central pontine myelinolysis, increase in seizure frequency, expansion of initial ICH, development of new ICH and/or stroke, development of new cardiac arrhythmia, development of pulmonary edema, change in renal function, and development of an infection.

Potential risks involving blood draws may include temporary discomfort from the needle stick, pain or bruising, lightheadedness, and infection at the site.

Potential risks of CT scans are exposure to radiation from X-rays, dizziness, cold sensation at injection site, worsening of poor kidney function, allergic reaction to injection dye, soreness or swelling at the injection site.

Potential risks will be minimized by blood pressure monitoring, monitoring of total Na⁺ mEq received, EEG monitoring and measurement (15-20% of patients with ICH have seizures, anti-seizure medications will be used), ICH/ICP monitoring, monitoring of troponin levels, chest x-ray and monitoring of pulmonary parameters (such as PO₂, FiO₂, A-a gradient), assessment of renal function by the RIFLE criteria, monitoring for infections.

Training sessions for all clinical study personnel will occur prior to the start of the study to discuss the potential risks that could occur, and the monitoring for and treatments that are in place.

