8.1 Data Reviewed

- Demographics: Age, race, gender, and risk factors (hypertension, diabetes, illicit drug use, coronary artery disease, stroke, alcohol use).
- Clinical Grading Scores:
 - Outcome: mRS (Appendix 2) at baseline and discharge (if available). This can be performed by study team or as part of normal clinical practice.
 - ICH score at baseline (Appendix 5).
 - GCS score at baseline, 24 hrs from enrollment, 72 hrs from enrollment 7 day and discharge (if available) (Appendix 4).
 - APACHE II at baseline (Appendix 3).
- Duration of Neruo-ICU and hospital stay.
- Need for any of the following:
 - EVD/Bolt.
 - Hemi-craniectomy.
 - Central venous line/PICC/Arterial line.
 - RRT.
- Concomitant osmotherapy:
 - Hypertonic saline. The total mEq delivered and form of delivery (i.e. NS vs. 3% NaCl solution vs 23.4% NaCl solution.)
 - Mannitol. Number of doses and total grams received.
- Concomitant medications
- Imaging evaluation: CT scans will be dichotomized and ICH volume and CE volume will be compared over time. The individual summed and averaged volumes, net ICH volume and edema volumes will be compared. A board certified/eligible radiologist will calculate serially

the hemorrhage volume on CT during the study period. ICH volume will be serially assessed both by the $(Ax \times B \times C)/2$ method and by volumetric calculations using volumetric software. Serial assessments of edema will occur by measurements of the length and width of regional edema in the CT slice demonstrating the greatest amount of edema. Volumetric calculations using volumetric software will also be employed to evaluate for CE volume. Further, the same measurements one slice above and below will be performed to allow for a volumetric comparison. Completed CT scan measurements and calculations will be e-mailed to the research coordinator for data entry. In addition to the planned imaging and chemistry panels, any other imaging or basic laboratory work, deemed medically necessary for patient care outside the study, will be evaluated in the final analysis.

Clinical data collected from time of ICU admission to day 7:

- Vital signs (BP, HR, Temp)
- Daily weights and admission height
- ICP/ CPP values- when available/when a monitor is being used
- CVP values- when available
- Volumes for intake and output.
- Na⁺ values
- Cl⁻ values
- Cr values
- BUN values
- PO₂ values- when available
- PCO₂ values-when available
- A-a gradient- when available

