The study population consists of patients with ICH at risk for developing CE.

a. Primary Objective – Safety and Tolerability

An evaluation of the safety assessment parameters of each of the seven (7) subjects will be done by the PI and Co-I during the patient's care. Should events occur regarding the administration of conivaptan that raise safety concerns, the PI has the authority to withdraw the subject and/or halt the study pending further investigation.

b. Secondary Objectives

Several secondary hypotheses can be tested for data generated by this investigation:

1. Reduction in CE as measured on CT. Goal is a 5-10% reduction in CE over time.
2. Patient outcomes: the modified Rankin Scale (mRS) will be used to assess patient outcomes at hospital discharge. This scale assess functional deficits on a scale from 0 (no deficit) to 6 (death).
3. Cost of care: Several proximal measures will be used to assess cost, including length of stay in the ICU, the need for EVD/bolt or surgical procedures to reduce or manage CE, the need for lines (central venous, arterial, PICC) or tracheostomy/PEGs, and the number of patients that required ventilation.

Study Endpoints

1. Laboratory values: assessment will end at the completion of conivaptan administration (Day 3).
2. Long-term Outcome: Patients will be observed for three months, beginning at enrollment, to determine long-term outcomes of conivaptan treatment.

4. Investigation Plan

This a single-center, open-label prospective study which aims to evaluate the safety and tolerability of conivaptan in patients with ICH that are at risk for developing CE. The study will include 7 patients with a diagnosis of ICH that is ≥ 20 cc in volume, aged between 18 – 80 years. All patients will receive 20mg IV of conivaptan every 12 hours equaling 40mg/day over 2 days (4 doses total), in addition to the standardized ICH management.

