All observations and assessments will be conducted as displayed in Table 1 of the Protocol. Patients will have CT scans at baseline and ~24, 72, and 168 hours (7 days) from enrollment to check for bleeding, lasting edema, or rebound edema. An 8 hour variance is permitted. It is preferable that the CT scans be done at 3mm increments as this is helpful for volume analysis, but 5mm is acceptable. Further imaging is left to the discretion of the treating/primary service physician. Electrolytes (standard-of-care, basic metabolic panel) for all subjects/patients will be measured every 12 hours for the first 72 hours of the study, and then daily after 72 hours. This is considered a regular schedule based on clinical need. However, during the ~48 hour period when the subjects are receiving conivaptan, a comprehensive metabolic panel, Mg, and PO₄ will be drawn and analyzed 6 hours after each conivaptan dose. These labs may be done sooner based on the patient's progress/need and/or the attending physician's direction. Neurological exams (e.g., EEGs), vital signs, and urine output measurements will be conducted as per Neuro-ICU protocol. The need for ancillary monitoring tools (i.e. EVDs, bolts, microdialysis, EEG, near-infrared spectroscopy) will be at the discretion of the treating physicians. Subjects will return for a 3 month follow-up assessment to assess neurological function and a final CT scan.

Study Duration: Each subject is expected to participate in the study for 7 days (including medication administration and wash-out) and the 3-month follow up.

Inclusion Criteria

- Age ≥ 18 years old and < 80 years.
- Diagnosis of primary ICH ≥ 20 cc in volume.
- Enrollment within 48 hours from initial symptoms.
- Signed informed consent from the patient or obtained via their legally authorized representative (if the patient is not able to sign the informed consent themselves). The patient's decisional capacity to either provide or refuse consent will be determined using the Glasgow Coma Scale (GCS), which is being assessed at baseline and at 24 hours (+/- 6hrs) after enrollment. A potential study participant with a GCS > 14 will be asked to provide their own initial study consent. A GCS ≤ 14 would indicate the need to pursue consent via legally authorized representative. Patient and/or LAR must be English speaking.

Exclusion Criteria

- Current need for renal replacement therapy (RRT).
- GFR of <30 mL/minute at time of admission.

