5.3 Evaluation of Objectives

Safety and tolerability will be assessed via the number of patients that experience abnormal seizure activity, show abnormal laboratory values, have increased infection rates, or exhibit an adverse events directly related to treatment with conivaptan. The change in CE volume will be reported as a measure of potential efficacy, and potential impacts on cost of care will be assessed by the length of stay in the ICU and the use of medical interventions to reduce CE volumes. Patient outcomes will be assessed using the mRS at discharge. Due to the small number of patients in this trial and absence of a control group, all evaluation will be descriptive only.

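### RIFLE is a primary renal safety measure, but Table 1 marks it at no time from Enrollment to Day 7 and no supplied text says what period the Discharge class covers

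*Protocol*

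**What the plan says.** Protocol 6.9, under renal tolerability, says "RIFLE criteria will be used to assess for development of renal dysfunction (Appendix 1". Protocol 7.1.1 counts "assessment of renal function by the RIFLE criteria" among the steps that reduce risk, without time points.

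Table 1 (Protocol 6.8) marks RIFLE at Baseline, Discharge and Follow-up. Footnote c covers the first two: clinical "assessments can be study only or standard-of-care activities with a time window of +/- 6 hours". Footnote i covers the third, with "information recorded, if available, from the electronic medical record". SAP 4 makes this table binding: "All observations and assessments will be conducted as displayed in Table 1 of the Protocol".

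The raw renal data are collected more often. Protocol 8.1 lists creatinine, BUN and intake/output under "Clinical data collected from time of ICU admission to day 7". Protocol 6.8 schedules routine chemistry every 12 hours to 72 hours and daily afterwards, plus a comprehensive metabolic panel 6 hours after each dose.

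The supplied SAP text does not name RIFLE. On laboratory values, SAP 3 says that "assessment will end at the completion of conivaptan administration (Day 3"). SAP 5.3 counts patients who, among other things, "show abnormal laboratory values, have increased infection rates, or exhibit an adverse events directly related to treatment with conivaptan", with no renal threshold.

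**The concern.** The stated purpose is to detect new renal dysfunction in patients given the drug. The stated schedule places the instrument before the first dose and again when the patient leaves, with nothing between. Read literally, it suits a measure of final status better than a measure of new injury.

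Renal safety is central to this trial's rationale. Protocol 6.7 argues that a new therapy should have side effects no worse than those of mannitol and hypertonic saline, and cites their renal effects. With seven patients and a descriptive analysis, the renal result is a count out of 7, and such a count depends entirely on its definition. Without a rule, two analysts working from the same charts could report different RIFLE counts: one classing each patient on the day of discharge, the other taking the worst class during the stay.

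**Working it through.** There is no plan figure to reproduce. The check is a count of Table 1 marks and a comparison of passages.

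**1. Columns.** Table 1 has 14 time columns. Enrollment is the 2nd and Day 7 the 12th, so Enrollment to Day 7 is 12 − 2 + 1 = 11 columns. They include all four doses.

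**2. Marks within those 11 columns.**

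| Row | Marks | Where |
|---|---|---|
| RIFLE | 0 | none |
| GCS | 3 | 24 h, 72 h, Day 7 |
| Comprehensive metabolic panel | 4 | 6 h after each dose |
| Intake/output | 4 | 24 h, 72 h, Days 3-6, Day 7 |
| Adverse event log | 11 | all |

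The panel and intake/output marks do not overlap, so 4 + 4 = 8 of the 11 columns carry a renal input.

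**3. Could the row be a conversion error?** Unlikely. It has 14 cells, like the other rows checked, and the same pattern as mRS. Protocol 8.1 independently gives baseline and discharge for mRS.

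**4. Could the windows close the gap?** No. A margin of 6 hours around Discharge does not create an assessment in the dosing period, and the Follow-up value depends on availability.

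**5. What the Discharge mark could mean.** The supplied text allows two readings:

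| Course of the patient | Same-day status | Look-back, worst class |
|---|---|---|
| Injury around dosing, resolved before discharge | not shown | shown |
| Injury still present at discharge | shown | shown |
| Death in hospital | no rule stated | classable from collected data |

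The readings differ in the first and third rows.

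**6. Laboratory cut-off.** Creatinine is collected to Day 7, but SAP 3 stops laboratory assessment at Day 3. Days 4, 5, 6 and 7 fall outside, which is 4 of 7 days. This limits the abnormal-laboratory-value count in SAP 5.3, which is one of the other places where renal injury could be seen.

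**7. How often would a rule for deaths be needed?** In-hospital mortality for this trial is not given. Assume 10% to 40%; the upper end is the 30-day figure that Protocol 3 cites for intracerebral hemorrhage in general. Expected deaths are 7 × 0.10 = 0.7 to 7 × 0.40 = 2.8. The chance of at least one is 1 − 0.90^7 = 52% to 1 − 0.60^7 = 97%. Under this assumption, a death is more likely than not.

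**The case against.** A reader might infer that RIFLE, as scheduled, reports renal status on the day of discharge in survivors only, so that the trial would overlook transient kidney injury. The documents do not support that.

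- No passage calls the Discharge mark a same-day snapshot. Table 1 supplies a Baseline reference, and 6.9 pairs RIFLE with change in renal function and urine output. A class entered at discharge from the serial chart fits that text equally well. Section 6.9 also has the investigators evaluating safety parameters during care.
- Restriction to survivors is an inference. SAP 3 assesses mRS at hospital discharge on a scale that includes death, so the Discharge column may cover in-hospital deaths.
- Appendix 1 was not available. It may contain a timing rule.
- Transient injury has another route. Protocol 7.2 treats an abnormal laboratory finding as a possible adverse event and asks for severity and onset and resolution dates. The adverse event log is marked in all 14 columns, and SAP 5.4 collects events whether or not related.
- The Day 3 cut-off concerns laboratory endpoints generally and is not tied to RIFLE.

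These points stand, and they limit the conclusion to an unstated derivation rule together with a schedule and cut-off that serve the purpose poorly. They do not remove it. The adverse event and laboratory routes have no stated renal threshold, and the adverse events counted in SAP 5.3 are those directly related to treatment. The Day 3 cut-off matters because it narrows one of those routes.

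It is also tempting to size the loss by calculation. Under the same-day reading, with injury rate p and share s resolved by discharge, the chance that RIFLE shows 0/7 is (1 − p(1 − s))^7. Assuming p of 10% to 30% and s of 25% to 75%, it runs from 17% to 84%. Neither rate comes from the documents, and no decision rule uses 0/7, so this is an illustration and not evidence of size.

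**Conclusion.** The concern holds in a limited form. The schedule marks RIFLE in 0 of the 11 columns from Enrollment to Day 7, the SAP's laboratory endpoint omits 4 of the 7 days of planned renal data, and the supplied text defines neither the period of the Discharge class nor the handling of deaths. RIFLE misses resolved injury only if the Discharge class is a same-day status.

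The gap lies in how the result is derived and reported, since the data are planned for collection. The number of patients affected cannot be estimated from the documents. The study is descriptive and unpowered, so no test or stopping boundary is affected; the readability of a primary safety count is. Confidence is moderate because Appendix 1 could settle the timing.

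**What to change.** In Table 1 and SAP 5.3, define the RIFLE safety result as the worst class from first dose to Day 7, or to discharge or death if earlier. Derive it from the creatinine and urine output already collected, relative to the Baseline value in Table 1 unless Appendix 1 fixes another reference.

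Report n/7 per class, with deaths included at their worst class before death. This agrees with SAP 5.1, which keeps all enrolled patients in one analysis set. Report the discharge and follow-up classes separately. Extend the SAP 3 laboratory cut-off to Day 7 for renal values, and reconcile Protocol 6.9, 7.1.1, Table 1 and SAP 3 on timing. If Appendix 1 already holds a look-back rule, refer to it in the SAP.

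The cost is low: one derived variable, with no new test or visit. The downside is minor derivation work and possibly a few more renal events reported, some unrelated to the drug.

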6.10 Secondary Assessments (Effectiveness)

- Reduction in CE as measured on CT. Goal is a 5-10% reduction in CE over time. Reduction will be measured both as absolute reduction, and as relative reduction, comparing the ratio of ICH to edema volume. The absolute edema reduction is more clinically relevant, while the ratio of ICH to edema volume has more research relevance, to aid in designing the next related studies.
- Outcome. mRS (Appendix 2) at discharge from ICU and from hospital stratified by APACHE II (Appendix 3), GCS (Appendix 4), and ICH Score (Appendix 5)
- Cost
 1. Length of stay in the neuro ICU.
 2. Need for EVD/bolt or surgical procedures (craniectomy, clot evacuation, VPS) for reduction/management of CE.
 3. Need for central venous lines, arterial lines, PICC lines, tracheostomy/PEGs.
 4. Duration on ventilator.
 5. Duration of EVD/bolt.

7. Safety Variables

7.1 Risks and Benefits

7.1.1 Potential risks

Potential risks associated with conivaptan may include hypotension, excessive rise in serum sodium, development of central pontine myelinolysis, increase in seizure frequency, expansion of initial ICH, development of new ICH and/or stroke, development of new cardiac arrhythmia, development of pulmonary edema, change in renal function, and development of an infection.

Potential risks involving blood draws may include temporary discomfort from the needle stick, pain or bruising, lightheadedness, and infection at the site.

Potential risks of CT scans are exposure to radiation from X-rays, dizziness, cold sensation at injection site, worsening of poor kidney function, allergic reaction to injection dye, soreness or swelling at the injection site.

Potential risks will be minimized by blood pressure monitoring, monitoring of total Na⁺ mEq received, EEG monitoring and measurement (15-20% of patients with ICH have seizures, anti-seizure medications will be used), ICH/ICP monitoring, monitoring of troponin levels, chest x-ray and monitoring of pulmonary parameters (such as PO₂, FiO₂, A-a gradient), assessment of renal function by the RIFLE criteria, monitoring for infections.

Training sessions for all clinical study personnel will occur prior to the start of the study to discuss the potential risks that could occur, and the monitoring for and treatments that are in place.

7.1.2 Potential benefits for the study subjects/society

Because the current medications used have their own side-effects, participation may result in better reduction of the patient's CE, and prevent/lessen the brain damage caused by CE/ICH, with less side effects from other typically used medications.

The patients enrolled would help demonstrate if conivaptan is safe, well-tolerated, and effective in patients with CE. This knowledge will help further the understanding of this therapy, and its role in treating CE, as well as assisting with the designing of future clinical studies.

